6.4 Determination of sample size

The most important aspect when selecting sites is their representativeness in each country. If 80% of NSCLC patients are being managed in large teaching hospitals, then 80% of the study sample should come from this type of hospital. Participating sites should include all the patients meeting inclusion/exclusion criteria during the inclusion period assumed to be 25-30 patients in a 6-months period, since there is no seasonal variability. (Estimated number of new lung cancer patients in large hospitals is 100-125/year).

Since the main objective is to obtain reliable information on how patients are being managed, it is essential to obtain valid information on all therapy lines. For this reason, and bearing in mind the high mortality of the disease, it is very important to have access to a sample large enough to finally provide a core group of patients likely to receive advanced treatment lines (including investigational products), and also to allow comparisons.

Assuming that generally in Central Eastern Europe and Russia 80-85%² of lung cancers are NSCLC, 80-90% of them are diagnosed at phase IIIb/IV (patients most likely to receive several lines of treatment) and of these 75-80% are treated (approximately 33% with investigational products). No published information is available regarding the proportion of these patients who will achieve further treatment lines, but for sample estimation we assumed that no more than 10% of newly diagnosed NSCLC patients would receive an active third line treatment.

It is estimated that approximately 4,000 patients will be included across several Central eastern European countries and Russia. This amount of patients would enable us to obtain a sample of approximately 400 IIIb/IV treated NSCLC patients throughout Europe.

For the descriptive analysis, 600 NSCLC phase IIIB-IV third line patients will allow us to estimate a proportion of 0.5 (taking into account that this is a novel study in NSCLC and the most pessimistic scenario must be considered) with a precision of 0.04, which means estimating 50% with a confidence interval from 46% to 54% (α =0.05).

It was also considered that the analytical objectives of the study would require multivariate analysis to determine the above sample size. This analysis will consider the main risk variables as independent variables. Based on the formula provided by Freeman²⁶ (the sample size must be 10 times the number of variables plus one) in order to perform such multivariate analysis, and having as variables for comparison: treatment, cycle, phase, primary tumour location, extent of disease, prior surgery, age, sex, EGFR markers, habits, PS/ECOG and type of hospital, the total sample size of 4,000 patients is advised.

Protocol of Non-Interventional Study Drug Substance: N/A

NIS Code: NIS-ORU-IRE-2009/1

Version No: 4.0 Date: 8 December 2009

A sample of 25% of patients per country will be included in the Quality of Life descriptive sub-study. Whether a sample from each site in the study is included in the sub-study will depend on the number of sites participating in each country. The number of sites involved will be determined bearing in mind that 25% of the total population included in the study must be invited to participate in the Quality of Life sub-study.

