Non-Interventional Stu	dv (NIS)	Protocol
------------------------	----------	----------

Drug Substance: N/A

NIS code: NIS-ORU-IRE-2009/1

Version No.: 4.0

Date: 8 December 2009

Epidemiological study to describe NSCLC clinical management patterns in Central Eastern Europe and Russia. Lung-EPICLIN

Sponsor:

AstraZeneca [name]

[contact] [contact]

The following Amendment(s) and Administrative Changes have been made to this Non-Interventional Study Protocol, since the date of preparation:

Amendment No.	Date of Amendment	Local Amendment No.	Date of Amendment	
		Addendum for Russia	08.12.2009	
Administrative change No.	Date of Administrative Change	Local Administrative change No.	Date of Administrative Change	

This submission /document contains trade secrets and confidential commercial information, disclosure of which is prohibited without providing advance notice to AstraZeneca and opportunity to object.

Version No: 4.0 Date: 8 December 2009

SUMMARY OF THE NON-INTERVENTIONAL STUDY PROTOCOL

Epidemiological study to describe NSCLC clinical management patterns in Central Eastern Europe and Russia. Lung-EPICLIN

National Coordinators

[name] Russian Cancer Research Center Department of Clinical Pharmacology and Chemotherapy [name]

[contact]

Protocol of Non-Interventional Study

Drug Substance: N/A

NIS Code: NIS-ORU-IRE-2009/1

Version No: 4.0 Date: 8 December 2009

Number of patients, sites and Countries (planned) in the study

It is estimated that 500 patients will be entered into the study from all over Russia.

Total planned study period

Estimated first patient in: 1st February 2010

Estimated last patient in: 1st August 2010

Estimated last patient out: 1st August 2011

Estimated database lock: 1 st October 2011

Medicinal product (type, dose, mode of administration) and concomitant medication (if applicable)

This is a purely observational study; therefore patients are not assigned to a particular therapeutic strategy beforehand by a protocol. Treatment will be according to current clinical practice.

Overall Aim for this Non-Interventional Study (NIS)

To provide accurate, reliable information on NSCLC clinical management across Central Eastern European countries and Russia in order to detect unmet medical needs of this disease in terms of:

- Patient and hospital characteristics.
- Diagnostic and treatment approaches: initial and subsequent.

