6. STATISTICAL METHODS AND DETERMINATION OF SAMPLE SIZE

6.1 Statistical evaluation – general aspects

All statistical analysis will be performed by the AstraZeneca Lung-EPICLIN Coordination Office and ALMEDIS CRO by means of the SAS® statistical software system.

The two-sided 95% confidence interval will be obtained for the population estimation of the variables

A comprehensive Statistical Analysis Plan (SAP) will be prepared before database lock.

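### Section 6.4 computes its precision on 600 third-line patients, but its own assumptions yield at most 400, so the stated ±4 points is at best ±4.9

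*Protocol*

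**What the plan says.** All the figures are in protocol section 6.4 (Determination of sample size), in this order:

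- Of NSCLC patients, 80-90% are taken to be stage IIIb/IV at diagnosis, and 75-80% of these to be treated.
- On third line: "we assumed that no more than 10% of newly diagnosed NSCLC patients would receive an active third line treatment".
- On the total: "It is estimated that approximately 4,000 patients will be included across several Central eastern European countries and Russia".
- On what that total yields: "This amount of patients would enable us to obtain a sample of approximately 400 IIIb/IV treated NSCLC patients throughout Europe".
- On precision, in the next paragraph: "For the descriptive analysis, 600 NSCLC phase IIIB-IV third line patients will allow us to estimate a proportion of 0.5", "with a precision of 0.04, which means estimating 50% with a confidence interval from 46% to 54" per cent, at α = 0.05. The proportion of 0.5 is chosen because "this is a novel study in NSCLC and the most pessimistic scenario must be considered".

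Section 6.1 fixes the confidence level: "The two-sided 95% confidence interval will be obtained for the population estimation of the variables". The protocol summary gives the Russian share of the cohort: "It is estimated that 500 patients will be entered into the study from all over Russia".

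**The concern.** The third-line assumption, the total and the number behind the precision statement cannot all hold. A ceiling of 10% applied to about 4,000 patients cannot produce 600, and the section does not say where the other 200 would come from. The yield sentence adds a second inconsistency: its 400 is described as treated IIIb/IV patients, yet it equals the 10% third-line yield and is far below the number of treated IIIb/IV patients that the section's own shares imply.

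This is the only precision statement in the protocol. The section also says that valid information on every line of therapy is essential, and third line is the scarcest group it considers. A reader would therefore expect a precision that the planned cohort does not deliver on the plan's own assumptions, and would be misled about how many treated advanced-stage patients to expect.

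**Working it through.** **Inputs.** From section 6.4: n = 600 third-line patients, p = 0.5, d = 0.04, third-line share at most 10%, N of about 4,000, stated yield of about 400, IIIb/IV share 80-90%, treated share 75-80%. From sections 6.1 and 6.4: two-sided 95%, so z = 1.96. From section 3.3.2.1: every enrolled patient already has confirmed NSCLC, so no reduction from lung cancer to NSCLC applies. From the summary: 500 patients in Russia.

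**1. The plan's own figure.** n = z² × p(1 − p) / d² = 1.96² × 0.25 / 0.04² ≈ 600.2. The half-width at 600 is 1.96 × √(0.25/600) = 0.0400. So 600 and ±0.04 agree with each other.

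**2. Third-line patients the plan can yield.** 4,000 × 0.10 = 400. As 10% is an upper limit, so is 400. The shortfall against 600 is at least 200 patients, or 200/600 = 33%.

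**3. Precision at 400.** 1.96 × √(0.25/400) = 0.0490, giving 45.1% to 54.9%. The exact (Clopper-Pearson) interval for 200 of 400 is 45.0% to 55.0%, so the choice of interval hardly matters.

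**4. What 600 would require.** At a 10% share, 600/0.10 = 6,000 enrolled. With 4,000 enrolled, 600/4,000 = 15% reaching third line. Neither figure appears in the protocol.

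**5. The label on the 400.** Treated IIIb/IV patients under the section's shares:
- lower end: 4,000 × 0.80 × 0.75 = 2,400
- upper end: 4,000 × 0.90 × 0.80 = 2,880

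That is 6.0 to 7.2 times the stated 400. Only the product in step 2 reproduces 400.

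**6. Other readings.**
- If the 10% applied only to IIIb/IV patients, the yield would be 4,000 × 0.80 × 0.10 = 320 to 4,000 × 0.90 × 0.10 = 360, with half-widths of 5.5 and 5.2 points.
- If the 4,000 were lung cancers of all types, the 80-85% NSCLC share would reduce the yield to 320-340.
- If 600 is a slip for 400, the 0.04 and the 46% to 54% interval are wrong instead.

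None of these restores ±4 points.

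**7. Russia, for orientation only.** 500 × 0.10 = 50 third-line patients at most; 1.96 × √(0.25/50) = 0.139, that is ±13.9 points at best.

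**The case against.** Several points on the other side have force.

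- **The loss is moderate.** The pooled half-width goes from 4.0 to 4.9 points, and only at the worst case of p = 0.5. At p = 0.2, 400 patients give 1.96 × √(0.16/400) = 0.039, within the stated 0.04. No test, error rate or decision rule depends on the figure. This stands and limits the size of the point, but the plan chose p = 0.5 itself and its stated interval is for that case.
- **Patients already treated elsewhere may enrol** (summary and section 3.1), whereas the 10% refers to newly diagnosed patients, so the true third-line share could be higher. This is possible, but the protocol gives no higher share for them and itself arrives at about 400.
- **Reading the 400 as the third-line yield is an inference.** It is. It rests on 10% × 4,000 matching exactly and on the treated IIIb/IV count being at least six times larger. The sponsor should confirm it.

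Two stronger readings are tempting and are not supported. A reader might infer that the ±4 points is the sole reason for enrolling 4,000, so that the whole sample size falls with it. Section 6.4 does not derive 4,000 from that target. It states 4,000 as an estimate and later supports it with a rule based on the number of variables in a multivariable analysis. A reader might also infer that Russian third-line results would be reported as too precise. The ±4 points is stated for the pooled sample and for no single country, and section 6.1 calls for confidence intervals on the estimates. These will come from the patients observed and will be wide if the patients are few.

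**Conclusion.** Section 6.4 is wrong as written. On its own figures the planned cohort yields at most 400 third-line patients, not 600, and the pooled 95% interval around 50% is at best 45.1% to 54.9%, not 46% to 54%. The 400 is mislabelled, or at least contradicts the section's own shares, which give 2,400 to 2,880 treated IIIb/IV patients.

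The conclusion assumes that all 4,000 are NSCLC patients, as the inclusion criteria require, that the 10% ceiling applies to all of them, and that patients count as independent observations. A third-line share below the ceiling, or clustering of treatment choices within sites, would widen the interval further; hence the words at best.

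The consequence is a planning statement that overstates precision by about 0.9 points in half-width, together with an unclear expected count. It does not invalidate the total of 4,000, and the small Russian third-line number contradicts nothing that the protocol claims.

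**What to change.** Reconcile 600, 10% and 4,000 in section 6.4. Only the sponsor can say which of the three is the slip.

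- If 4,000 and 10% are kept: replace 600 with at most 400 third-line patients, and replace ±4 points (46% to 54%) with at best ±4.9 points (45.1% to 54.9%).
- If 600 is kept: justify either 6,000 enrolled or a third-line share of 15% among 4,000.
- Under the first option, relabel the 400 as third-line patients and give 2,400 to 2,880 as the expected number of treated IIIb/IV patients.
- Optionally, add one sentence saying that the stated precision is for the pooled sample, and that 500 Russian patients would yield at most 50 in third line (±13.9 points at best).

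The first option costs a rewording of one section and a slightly less favourable stated precision, with no extra patients. Keeping 600 by enlarging the cohort would cost 2,000 more patients at the 10% share (6,000 − 4,000).

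### The multivariate sample-size rule in section 6.4, applied to its 12 listed variables, gives 121 or 130 patients and does not lead to the 4,000 attributed to it

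*Protocol*

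**What the plan says.** Section 6.4 of the protocol gives 4,000 twice. It first appears as expected recruitment: "It is estimated that approximately 4,000 patients will be included across several Central eastern European countries and Russia". The section assumes that "no more than 10% of newly diagnosed NSCLC patients would receive an active third line treatment" and adds: "This amount of patients would enable us to obtain a sample of approximately 400 IIIb/IV treated NSCLC patients throughout Europe". A precision statement follows, based on a different number: "600 NSCLC phase IIIB-IV third line patients will allow us to estimate a proportion of 0.5", with a half-width of 0.04.

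The second appearance is the one at issue. As a further consideration, the section says the analytical objectives need multivariate analysis and cites a rule under which "the sample size must be 10 times the number of variables plus one". The variables are "treatment, cycle, phase, primary tumour location, extent of disease, prior surgery, age, sex, EGFR markers, habits, PS/ECOG and type of hospital". From the rule and this list it concludes that "the total sample size of 4,000 patients is advised".

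**The concern.** Rule, inputs and result stand in one sentence, so a reader can check them directly, and they disagree by more than an order of magnitude. The section gives no count of model parameters, interactions, subgroup multiplier or event rate that would link them.

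What is at stake is the justification, not patient numbers. Someone judging whether the cohort can support the regression models of sections 6.2 and 6.3 is told that 4,000 was derived from the needs of those models. The calculation shown does not establish that, and it does not say what size of model the cohort was meant to carry.

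**Working it through.** **Inputs, all from protocol section 6.4**
- Rule: ten times the variable count, plus one. The wording allows 10k + 1 or 10(k + 1).
- k = 12: treatment; cycle; phase; tumour location; extent; prior surgery; age; sex; EGFR markers; habits; PS/ECOG; hospital type.
- Stated result: 4,000.
- Third-line share: at most 10%.

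**Attempt to reproduce 4,000**
- 10k + 1 = 10 × 12 + 1 = 121.
- 10(k + 1) = 10 × 13 = 130.
- Ratios: 4,000 / 121 = 33.1 and 4,000 / 130 = 30.8.
- Inverted: 4,000 / 10 − 1 = 399 variables under the second reading, and (4,000 − 1) / 10 = 399.9 under the first.

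**Rule required within the third-line group**
- 121 / 0.10 = 1,210 and 130 / 0.10 = 1,300.
- Ratios: 4,000 / 1,210 = 3.3 and 4,000 / 1,300 = 3.1.
- The 10% is an upper bound, so a smaller share would raise these totals. Reaching 4,000 would need a share of 121 / 4,000 = 3.0% or 130 / 4,000 = 3.25%. The section gives no such figure, and its own 400 out of 4,000 corresponds to 10%.

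**Other routes, each needing an assumption the section does not state** (10(k + 1) reading)
- All two-way interactions: 12 + 66 = 78 terms, 10 × 79 = 790.
- Three-way interactions as well: 78 + 220 = 298 terms, 10 × 299 = 2,990.
- Two, three, four or five parameters per variable: 250, 370, 490 or 610; divided by 0.10, these become 2,500, 3,700, 4,900 or 6,100.
- 39 parameters (39 / 12 = 3.25 per variable) within third line: 10 × 40 = 400, and 400 / 0.10 = 4,000.
- Separate models for three stage groups within third line: 3 × 130 / 0.10 = 3,900.

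The last two routes reach or approach 4,000, but only with inputs chosen to do so. The three-stage route also fits badly: the section describes the third-line patients as IIIB-IV, and phase and extent are already among the covariates.

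**The other strand of section 6.4**
- 4,000 × 0.10 = 400. The text labels the 400 as treated IIIb/IV patients. I read them as the third-line group, because the section's shares for stage and treatment would give 4,000 × 0.80 × 0.75 = 2,400 to 4,000 × 0.90 × 0.80 = 2,880 treated IIIb/IV patients.
- Precision at p = 0.5: n = 0.25 × (1.96 / 0.04)² ≈ 600, so the 600 is right for a half-width of 0.04.
- At 10%, 600 third-line patients need 600 / 0.10 = 6,000 enrolled.
- With 400 patients the half-width is 1.96 × √(0.25 / 400) = 0.049.

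**The case against.** The strongest reply is that the rule is not the main basis for 4,000. It is introduced as an additional consideration, after 4,000 has been given as expected recruitment and linked to a core group of about 400. A rule of this kind sets a floor, and 4,000 clears 130 about 31 times over. This stands. It confines the point to the multivariate attribution and makes it an error of documentation.

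A second reply is that the factor of 31 to 33 depends on applying the rule to the whole cohort. If it has to hold among third-line patients, the gap is about threefold, and at 39 parameters it closes. This stands as a caution about the size of the discrepancy. It does not rescue the text, because the section states neither the parameter count nor the subgroup.

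A third reply is that detail belongs in the statistical analysis plan that section 6.1 promises. That is fair for variable coding, term counts and event-based limits, none of which is part of the quoted rule, and I raise no point on them. It does not cover a formula, inputs and result that the protocol itself states and that disagree.

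A reader might also infer that the rule fails in Russia. The summary says "It is estimated that 500 patients will be entered into the study from all over Russia", and 10% of 500 is 50, below 121. The documents do not support this as a finding. Sections 6.2 and 6.3 group patients by baseline stage and fit models without restriction to third line, and no Russian third-line model is planned. The whole Russian cohort of 500 is above 130.

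**Conclusion.** The point holds as an arithmetic error in section 6.4. The quoted rule with the 12 listed variables gives 121 or 130, or 1,210 to 1,300 if it must be met within a 10% third-line share, and not 4,000. This assumes one model term per listed variable, as the rule is worded; no other input stated in the section bridges the gap.

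Two stronger conclusions should not be drawn. The study is not too small by this rule, since 4,000 satisfies it. Nor does the error show by itself that 4,000 is the wrong target, only that this calculation does not produce it. The other strand cannot simply take its place, however: it expects about 400 third-line patients while its precision statement assumes 600, and 400 give about ±0.049, not ±0.04.

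**What to change.** In section 6.4, do one of the following:
- Stop attributing 4,000 to the rule. Say which reading is meant, and state that for 12 single-term variables it requires at least 121 (or 130) patients, which the planned 4,000 exceeds.
- If 4,000 did come from this rule, state the number of model parameters and the subgroup in which the rule has to hold, and show the arithmetic that leads to 4,000.

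Do not replace the sentence with a claim that third-line yield sets the 4,000 until the 400 expected and the 600 assumed are reconciled, either by restating the precision for 400 (about ±0.049) or by explaining how 600 would be reached.

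The first option costs a rewording of one paragraph; the second also requires recovering the assumptions used. Neither changes enrolment or the planned analyses.

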7. STUDY MANAGEMENT

7.1 Monitoring and Quality Control

Before the first patient is recruited into the study, the local AstraZeneca MC representative or delegate will:

- Establish the adequacy of the facilities and the investigator's capability to appropriately select the sample.
- Discuss with the investigator(s) (and other personnel involved in the study) their responsibilities with regards to protocol compliance, and the responsibilities of AstraZeneca or its representatives. This will be documented in a Study Agreement between AstraZeneca/delegate and the investigator.

During the study the local MC representative or delegate may implement several activities to assure compliance with AZ standards of quality. These activities could include but are not limited to:

- Contacts with the sites to:
 - Provide information and support to the investigator(s),
 - Confirm that the investigational team is complying with the protocol and data are being accurately recorded in the electronic case report forms (eCRFs).
 - Ensure that the informed consent form is signed and stored at the investigator's site (only if required, see above).
- Monitoring activities for:
 - Checking a sample of ICFs (only if required).
 - Checking that patients exist by reviewing the existence of their medical records (a sample).
 - Different signals (e.g., high rejection rate in a site) should be used as possible triggers for low protocol compliance by investigators. Low rate of NSCLC patients (number of NSCLC identified patients/total number of patients

Version No: 4.0 Date: 8 December 2009

attending the clinic) in the identification period, compared with the expected prevalence.

If these, or any other signal occurs or if the local coordinator is suspicious of a potential non-optimal level of protocol compliance by the site investigator, specific measures should be adopted to evaluate the situation, identify the issue and implement specific action plans to correct the situation. These mechanisms should be agreed with the Steering Committee.

In a random sample of sites (10% in each country), a qualified, trained individual other than the Principal Investigator (preferably a CRA) should monitor all the patients included in the study at the selected sites (in terms of ICF collection). This procedure should be performed after 50% of the expected sample is already included.

7.2 **Training of staff**

The principal investigator will keep a record of all staff members involved in the study (medical, nursing and other staff). He/she will ensure that all staff receive appropriate training relevant to the study, and that any new/relevant information is forwarded to the staff involved.

